**7.9.6 Visit 5 (Day 43) or 6 (57) (if required)**

If HPA axis is suppressed at End of Treatment Visit, another test will be administered at approximately Day 43 (for 15-day treatment groups) or Day 57 (for 29-day treatment group) to confirm recovery. The ACTH stimulation test will be repeated approximately every 28 days until HPA axis is stabilized (or explained).

1. Collect vital signs (blood pressure, pulse).

---

2. Perform urine pregnancy test for female subjects. Test must be negative to proceed with the ACTH stimulation test.
3. Conduct ACTH stimulation test. The entire test, including pre- and post-stimulation blood and saliva samples, should be completed between approximately 7:00 am and 9:30 am.
4. Collect adverse event data.
5. Update concomitant medications data.
6. Complete CRF.

## **8 ADVERSE EVENTS**

Adverse events will be collected by spontaneous reports from subjects and legal guardians, either verbal or recorded in the subject diary, by directed questioning of subjects, and by observation.

Adverse events associated with the use of topical betamethasone dipropionate include erythema, folliculitis, pruritus, and vesiculation each occurring in less than 1% of patients.

In addition, the following additional local adverse reactions have been reported with topical corticosteroids, and they may occur more frequently with the use of occlusive dressings and higher potency corticosteroids. These reactions are listed in an approximately decreasing order of occurrence: burning, itching, irritation, dryness, folliculitis, hypertrichosis, acneiform eruptions, hypopigmentation, perioral dermatitis, allergic contact dermatitis, secondary infection, skin atrophy, striae, and miliaria.

The investigator is to pay special attention at each post-treatment visit to any signs of clinically significant atrophy or telangiectasia and report presence as an adverse event if severity is worse than baseline. The investigator will also ask the subject if any burning/stinging, pain, or itching has occurred in the treated areas since the last visit (for Visit 2 in the last 14 days). Baseline assessments are made prior to first application. Subsequent to the Baseline Visit, for each symptom reported by subjects and/or each clinically significant sign, the presence of the sign or symptom must be recorded as "Yes" even if severity is not worse than Baseline. An adverse event should be recorded if the severity is worse than Baseline.

An adverse event is any untoward medical occurrence in a subject participating in a clinical trial. The event does not necessarily have to have a causal relationship with the study product. An adverse event can therefore be any sign, symptom, or disease, or any worsening of an existing sign, symptom, or disease, whether or not considered related to the study product or trial procedures, including injuries.

Any medical condition that is present at the time of Screening or Baseline should be considered as medical history and reported on the medical history CRF and should not be reported as an adverse event except for adverse events observed at the Baseline Visit due to study procedures performed at the Screening Visit which should be reported (except for worsening of psoriasis). Anticipated day-to-day fluctuations of pre-existing conditions should not be reported as adverse

---

events. Unexpected worsening of pre-existing conditions should be reported as adverse events. The disease or condition being studied or expected progression, signs, or symptoms of the disease or condition being studied should not be reported as an adverse event unless more severe than expected.

All serious adverse events, all study-product-related adverse events and all adverse events leading to study product discontinuation must be followed until the clinical outcome is determined or until all attempts to determine resolution of the event are exhausted (“not recovered” is not an acceptable outcome for acute conditions). For other adverse events, the status at the last visit can be entered into the CRF.

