### **7.9.1 Visit 1 - Screening Visit (60 days or less from Baseline Visit 2)**

1. Obtain written informed consent from legal guardian and written assent from subject prior to completing any study procedures. Document informed consent and assent in the subject's study record.
2. List subject on Screening/Enrollment Log. Assign subject number consisting of the 3 digit site number followed by sequential 3 digit numbers starting with 001 (e.g. 400001, 400002, 400003, etc.).
3. Collect demographic data – date of birth, sex, race, weight, and ethnicity.
4. Review and record medical history and concomitant medications, therapies and procedures. Medical history should be collected for the prior 1 year period and concomitant medications, therapies and procedures collected from the prior 2 month period. (record on source only)
5. Screen subject according to the study inclusion/exclusion criteria to determine tentative eligibility.
6. Initiate any protocol required washout.
7. Assess severity of psoriasis using IGA (record on source only).
8. Assess BSA excluding face, scalp, axillae, groin and other intertriginous areas. (record on source only)
9. Collect vital signs (blood pressure, pulse). (record on source only)
10. Conduct urine pregnancy test (UPT) for all female subjects (record on source only). Test must be negative to proceed.
11. If tentatively eligible and UPT is negative, conduct ACTH stimulation test (approximately 10 mL of blood is required). This test should be conducted at least 14 days and no more than 28 days prior to Visit 2 (Baseline). The entire test, including pre- and post-stimulation blood and saliva samples, should be completed between approximately 7:00 am and 9:30 am. Schedule for another day if needed. Also a screening PK blood sample will be drawn to obtain a baseline value. Blood (approximately 6 ml) will be collected in NaF/Na2EDTA blood collection tubes for PK analysis.

**Note:** Subjects with an abnormal ACTH stimulation test (cortisol level  $\leq$  18 ug/dL at 30 minutes post stimulation) should be referred to their primary care physician, as needed.

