### **7.9.2 Visit 2 - Day 1 - Baseline Visit**

1. Update the medical history and concomitant medications. Any medical event (not related to a protocol intervention) that occurred since informed consent was signed should be recorded as medical history if still ongoing.
2. Collect adverse events. Any new medical event, need for new medication, or change in medication dosing caused by a protocol procedure performed at the Screening Visit should

be considered an adverse event except for worsening of psoriasis.

3. Confirm eligibility according to inclusion/exclusion criteria.
4. Conduct urine pregnancy test on female subjects. Record method of contraception, as applicable, on source only.
5. Collect vital signs (blood pressure, pulse).
6. Conduct clinical assessments:
  - a. IGA ([Table 2](#))
  - b. Local cutaneous safety evaluation for clinically significant atrophy and telangiectasia in areas to be treated. The investigator should also ask the subject if any burning/stinging, pain, or itching has occurred in the areas to be treated in the last 14 days.
  - c. Diagram affected areas to be treated (excluding face, scalp, axillae, groin and other intertriginous areas).
  - d. Determine BSA excluding face, scalp, axillae, groin and other intertriginous areas.
7. Randomize the subject by referring to the randomization schedule and dispense study product to the subject/legal guardian. The tear-off panel from the box is to be affixed to the source document. Make a note on source document regarding treatment duration.
8. Instruct subject and legal guardian on study product use. Review the appropriate Subject Instructions with subject (See [Appendix 2](#)). Using the diagram of affected areas, have the subject treat the affected areas under supervision after weighing the study product.
9. Dispense and review use of diary. Remind subject and legal guardian to record actual application dates and/or potential adverse events as well as any medication used in the diary and to bring diary to each visit.
10. Schedule next visit.
11. Complete CRF for all subjects including screen failures. Only enter concurrent medical conditions and concomitant medications on the CRF.

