### **8.1 Adverse Event Reporting Period**

Adverse event data must be collected from the time treatment is initiated until study product treatment is discontinued except for spontaneously reported serious adverse events which should be reported up to 30 days after discontinuing study product use and entered on the CRF. Adverse events occurring from the time of the Screening Visit until the Baseline Visit associated with study procedures should also be reported for all subjects including screen failures. Abnormal screening ACTH stimulation test should not be reported as an adverse event. Abnormal End of Treatment ACTH stimulation tests will be recorded as adverse events of HPA axis suppression related to study product and will be repeated until HPA axis is stabilized (or explained).

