#### **8.3.3 Seriousness**

It is the investigator's responsibility to determine the "seriousness" of an adverse event. A serious adverse event (SAE) is any adverse event occurring at any dose that results in any of the following outcomes:

---

1. Death
2. Life-threatening (subject at immediate risk of death)
3. Inpatient hospitalization or prolongation of hospitalization
4. Results in persistent or significant disability/incapacity
5. Results in congenital anomaly/birth defect

Important medical events that may not result in death, are not life-threatening, or do not require hospitalization may be considered an SAE when, based upon appropriate medical judgment, they may jeopardize the subject and may require medical or surgical intervention to prevent one of the outcomes listed above. Examples of such medical events include allergic bronchospasm requiring intensive treatment in an emergency room or at home, blood dyscrasias or convulsions that do not result in inpatient hospitalization, or the development of drug dependency or drug abuse.

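### Reporting rules for worsening psoriasis between Screening and Baseline conflict, so a serious flare during washout could go unreported as an SAE

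*Combined protocol and SAP*

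**What the plan says.** Five parts of the protocol bear on this.

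- **Start of washout.** Section 7.9.1 step 6 tells the site: "Initiate any protocol required washout". Exclusion criteria 4, 5 and 7 in section 5.3 set the drug-free periods before Baseline. They are 60 days for immunosuppressive, systemic antipsoriatic and biologic treatment, 30 days for topical antipsoriatics, light therapy and systemic anti-inflammatory agents, and 14 days for topical retinoids.
- **The exception.** Section 8 treats conditions present at Screening or Baseline as medical history, apart from events seen at Baseline that are due to "study procedures performed at the Screening Visit which should be reported (except for worsening of psoriasis". Section 7.9.2 step 2 says that a new event caused by a Screening procedure should "be considered an adverse event except for worsening of psoriasis".
- **General sentences in section 8.** The adverse event definition includes "any worsening of an existing sign, symptom, or disease, whether or not considered related to the study product or trial procedures". Section 8 also says "Unexpected worsening of pre-existing conditions should be reported as adverse events", and that the disease under study "should not be reported as an adverse event unless more severe than expected".
- **Reporting period.** Section 8.1 opens: "Adverse event data must be collected from the time treatment is initiated until study product treatment is discontinued". It then adds that events associated with study procedures between Screening and Baseline are also reported, for screen failures too. The only Screening finding it exempts is an abnormal ACTH test.
- **Seriousness.** Section 8.3.3 states: "A serious adverse event (SAE) is any adverse event occurring at any dose that results in any of the following outcomes". Section 8.4 requires an SAE report within 24 hours and names no psoriasis exclusion.

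**The concern.** Stopping effective psoriasis treatment in order to enter the trial can foreseeably worsen the disease. None of the other Screening steps (assessments, blood and saliva sampling, a pregnancy test, one ACTH test) is an obvious cause of a flare. The exception therefore appears to fall on the harm one would expect from washout, and it does so without regard to seriousness.

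The subjects are aged 12 to 16.9 years. If a flare that meets section 8.3.3 is not recorded as an adverse event, no 24-hour report follows. The judgement under section 7.8 on whether the study poses an unreasonable risk might then be made without it. Two sites following the same protocol could also handle the same hospitalized subject differently, one filing an SAE report and the other entering only a reason for screen failure.

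**Working it through.** No arithmetic applies. The check is to read sections 7.9.1, 7.9.2, 8, 8.1, 8.3.3 and 8.4 together and follow one event through them: a psoriasis flare during washout that leads to inpatient hospitalization.

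1. **SAE status depends on adverse event status.** Section 8.3.3 defines an SAE as an adverse event with a listed outcome, and section 8.4 applies only to SAEs. The question is therefore whether the flare counts as an adverse event.

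2. **The answer depends on two points the protocol leaves open:** which sentence prevails, and whether washout is a study procedure.

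| Reading | Route through the text | Result |
|---|---|---|
| A. Washout is a procedure, the subject attends Baseline, the exception prevails | 7.9.2 step 2 and the exception in 8 | Not an adverse event, so not an SAE |
| B. As A, but the general sentences in 8 prevail | Unexpected, or more severe than expected | Adverse event, and SAE because of hospitalization |
| C. Washout is a procedure, the subject never reaches Baseline | The exception concerns findings at Baseline and a Visit 2 step; 8.1 covers screen failures | Reportable on the more natural reading |
| D. Washout is not a procedure | The exception and the pre-Baseline clause of 8.1 both fall away; 8.1 otherwise starts at first treatment, and 7.9.2 step 1 records ongoing events as medical history | Probably not reported |

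3. **The general sentences do not settle reading B for every serious case.** They ask whether worsening was unexpected or more severe than expected. Section 8.3.1 (severity) and section 8.3.3 (seriousness) are separate assessments. An investigator could judge a marked flare after withdrawal of a systemic or biologic drug to be expected, and the hospitalization would then fail the test. Neither general sentence says that it overrides the specific exception, and section 7.9.2 contains no such test.

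4. **Other records recover the event only in part.** Screening IGA and BSA are kept in source documents only (section 7.9.1 steps 7 and 8). Medications taken before Baseline need not be entered on the CRF (section 6.6). For a screen failure, section 7.2 lists the subject number, two dates, the status and a reason.

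5. **Effect on the analyses.** Such events precede the first dose. They lie outside the treatment-emergent definition in section 11.5.5 and do not enter the cortisol proportion in section 11.5.3. The output that could be incomplete is the section 11.5.5 listing of procedure-related events before study product.

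**The case against.** A reader might infer that no serious flare before Baseline would be reported, and that the sponsor could not learn of one. The documents do not support that reading.

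- Section 8.1 governs this period, names screen failures and has no psoriasis exception. A subject hospitalized before Baseline who never attends that visit is not plainly covered by the exception (reading C).
- The same section that contains the exception keeps unexpected and more-severe-than-expected worsening reportable, and does not limit those sentences to the period after Baseline. A hospitalized flare would plausibly qualify.
- The protocol never calls washout a study procedure. If it is not one, the exception is beside the point, and the gap lies in section 8.1 and the medical-history rule.
- The reason for every screen failure reaches the CRF and the log (sections 7.2 and 9.3), and monitors visit the sites (section 10). The sponsor is not blind to such a case.
- Conversion to a form listed in exclusion criterion 1 is not clearly worsening of plaque psoriasis, and is not serious in itself unless it meets section 8.3.3.
- Setting 60 days of washout against 15 or 29 days of treatment compares window lengths. It measures neither risk nor under-reporting, and 60 days applies only to some drug classes.

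All of this stands against a claim of certain non-reporting. It does not remove the conflict. Section 8.1 still speaks of adverse events, a status that section 7.9.2 denies to worsening psoriasis. The rescuing sentences turn on expectedness, and a screen-failure reason is no substitute for a 24-hour SAE report.

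**Conclusion.** The point holds as a conflict in the safety-reporting rules. Section 7.9.2 step 2 and section 8 except worsening of psoriasis without regard to seriousness. Other sentences in section 8, and section 8.1, point the other way, and nothing says which prevails or how washout is classed. A serious flare during washout could therefore go unreported as an SAE. Readings A and D lead to that result, while B (if the flare is judged unexpected or more severe than expected) and C lead to a report.

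The size cannot be put in numbers, because the documents do not say how many subjects will need washout or how often a serious flare is expected. The conclusion assumes only that some subjects will stop prohibited treatment after consent, which section 7.9.1 step 6 and section 7.1 provide for. The primary cortisol result and the treatment-emergent tables do not depend on it. It is still worth correcting, because the risk arises from entering the trial, the subjects are minors, and the remedy is cheap.

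**What to change.** Change the wording in three places.

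- **Section 7.9.2 step 2 and section 8:** limit the exception to non-serious worsening of psoriasis.
- **Section 8.1:** state that events associated with protocol-required washout count as associated with study procedures. Add that any event meeting section 8.3.3 between consent and Baseline, including worsening of psoriasis, is reported under section 8.4 for all consented subjects, screen failures included.

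Conversion to another form of psoriasis should be reported as an SAE only if it meets section 8.3.3; no new SAE category is needed. Editing the exception alone would not be enough, since it would leave the gap in section 8.1 if washout is held not to be a procedure.

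The cost is a small number of extra reports, mostly from screen failures. No new visits, forms or analyses are required, and the additional events can go into the pre-treatment listing already planned in section 11.5.5.

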### **8.1 Adverse Event Reporting Period**

Adverse event data must be collected from the time treatment is initiated until study product treatment is discontinued except for spontaneously reported serious adverse events which should be reported up to 30 days after discontinuing study product use and entered on the CRF. Adverse events occurring from the time of the Screening Visit until the Baseline Visit associated with study procedures should also be reported for all subjects including screen failures. Abnormal screening ACTH stimulation test should not be reported as an adverse event. Abnormal End of Treatment ACTH stimulation tests will be recorded as adverse events of HPA axis suppression related to study product and will be repeated until HPA axis is stabilized (or explained).

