**Study Schedule ( 29-day treatment arm)**

	Visit 1	Visit 2	Visit 3	Visit 4	Visit 5	Visit 6
	Screen a	Day 1 (Baseline)	Day 8 b	Day 15 b	Day 29 b (End of Treatment)	Day 57 c
Informed Consent	X					
Collect Demographic Data	X					
Inclusion and Exclusion Criteria	X	X				
Med History / Prior & Con Meds	X	X				
Vital Signs (BP, Pulse)	X	X	X	X	X	X
Urine Pregnancy Test	X d	X	X	X	X d	X d
Determine BSA	X	X			X	
IGA	X	X	X	X	X	
ACTH stimulation test g (blood and saliva samples)	X e				X h	X i
Local Cutaneous Safety Evaluation		X	X	X	X	
Randomization		X				
Weigh and Dispense Medication (as needed)		X	X	X		
Supervised treatment		X			X k	
Take Blood Samples for PK j	X				X	
Dispense/Review/Collect Study Diary		X	X	X	X	
Diagram affected areas to be treated		X	X	X		
Review Subject Instructions		X	X	X	X	
Collect and Weigh Used Containers			X	X	X	
Evaluate Compliance			X	X	X	
Review Concomitant Medications		X	X	X	X	X
Adverse Event Assessment		X f	X	X	X	X
End of Study					X	X

a No more than 60 days before Visit 2

b Allowed visit window  $\pm$  3 day

c If needed due to abnormal ACTH test result at End of Treatment Visit

d Pregnancy test just prior to ACTH stimulation test

e At least 14 days, and no more than 28 days, prior to Day 1

f Related to study procedures only

g ACTH stimulation test to be performed between 7:00 and 9:30AM

h ACTH stimulation test should be performed within 1 hour of time of when Screening test was performed

i ACTH stimulation test will be repeated until recovery (or is explained)

j Blood will be drawn at the time of the screening pre-stimulation ACTH test and at 0, 1, 3, 6 hours (+/-5 minutes) after application at End of Treatment Visit

k Weigh bottle before and after application

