**Sample Analysis**

The determination of the serum and saliva cortisol levels will be estimated by a validated method. A normal response is defined as a serum cortisol level of more than 18 ug/dL at 30 minutes post-stimulation. An abnormal response at end of treatment should be recorded as an adverse event of HPA axis suppression.

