### **8.2 Recording Adverse Events**

The investigator will record all adverse events, regardless of relationship to study product on the adverse event CRF. Standard medical terminology should be used when describing adverse events. Whenever possible a diagnosis should be made and recorded on the CRF rather than listing signs and symptoms. Intermittent adverse events can be recorded once. The anatomical location of the adverse event must be specified, when applicable, as well as whether the location is a treatment area. The following information should be recorded on the CRF:

1. Description
2. Start date
3. Stop date or date of death, ongoing, or unknown
4. Severity of the event (see [8.3.1: Severity](#) for details)
5. Study product use continued or not
6. Outcome of the event (recovered/resolved, recovered/resolved with sequelae, not recovered/not resolved, unknown, fatal)
7. Relationship to study product (see [8.3.2: Relationship to Study Product \(Causality\)](#) for details)
8. Indication of whether the event is serious (see [8.3.3: Seriousness](#) for details)
9. Actions taken including treatment with concomitant medication

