### **11.5.5 Adverse Events**

All AEs occurring during the study will be recorded and classified on the basis of MedDRA terminology. Treatment-emergent adverse events are those AEs with an onset on or after the date of the first study product administration. For the safety population, all reported treatment-emergent AEs will be summarized by treatment group, the number of subjects reporting events, system organ class, preferred term, severity, relationship to study product, and seriousness. When summarizing AEs by causality and severity, each subject will be counted only once within a system organ class or a preferred term by using the event with the greatest relationship and highest severity within each classification.

Serious adverse events (SAEs) will be summarized by treatment group, severity, and relationship to study product, and SAEs will be listed by subject. In addition, a list of subjects who prematurely discontinued from the study due to an AE will be provided.

All information pertaining to AEs noted during the study will be listed by subject, detailing verbatim term given by the investigator, preferred term, system organ class, onset date,

---

resolution date, maximum severity, seriousness, action taken regarding study product, corrective treatment, outcome, and drug relatedness. The event onset will also be shown relative (in number of days) to date of first administration.

AEs related to study procedures done before study product administration will be provided in a data listing.

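### Section 8.1 stops non-serious adverse event collection at the end of treatment, but the Day 43/57 visit, attended only by suppressed subjects, collects events without limit, and the treatment-emergent definition has no end date

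*Combined protocol and SAP*

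**What the plan says.** Section 8.1 sets the general rule: "Adverse event data must be collected from the time treatment is initiated until study product treatment is discontinued except for spontaneously reported serious adverse events". The exception for serious events runs on: "which should be reported up to 30 days after discontinuing study product use". It names no other post-treatment collection of new events.

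Section 7.9.6, step 4, for the conditional visit at Day 43 (15-day arm) or Day 57 (29-day arm), says only "Collect adverse event data". Both study schedules mark the Adverse Event Assessment row at that visit. The one limiting footnote in that row is on Day 1, where it restricts collection to events related to study procedures. The Day 43/57 cell carries no limit.

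Footnote c in both schedules defines who attends: "If needed due to abnormal ACTH test result at End of Treatment Visit".

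Section 11.5.5 defines the analysis set of events: "Treatment-emergent adverse events are those AEs with an onset on or after the date of the first study product administration". All such reported events are tabulated by treatment group. No end date is given. For the listings, the section adds: "The event onset will also be shown relative (in number of days) to date of first administration".

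Three other provisions bear on the size of the problem. Section 7.5.1 (Sample Analysis) says "An abnormal response at end of treatment should be recorded as an adverse event of HPA axis suppression", and 8.1 adds that this event is recorded as related to study product. Section 8.2 says "Whenever possible a diagnosis should be made and recorded on the CRF rather than listing signs and symptoms". Section 8 requires serious events, product-related events and events leading to discontinuation to be followed to outcome.

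**The concern.** A site cannot tell from the text whether a new, non-serious event first found at Day 43 or 57 should be recorded. Section 8.1 says no; 7.9.6 and the schedules, read plainly, say yes.

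The choice matters because attendance depends on the primary safety variable. Subjects with a normal End of Treatment test have no later visit and are not asked again. Suppressed subjects are asked at least once more, and possibly at further retests about every 28 days. If their late events are recorded, 11.5.5 as written places them in the same by-arm rows as events from subjects whose observation ended at the End of Treatment Visit. If they are not recorded, new and separately diagnosed non-serious events during recovery are lost. If sites differ, both happen in one table. In a study of 25 adolescents per arm whose output is descriptive, one subject is 1/25 = 4 percentage points of a row.

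**Working it through.** **The texts side by side**

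| Question | 8.1 | 7.9.6 and schedules | 11.5.5 |
|---|---|---|---|
| New non-serious event after product stops | Not collected | Adverse event data collected at Day 43/57, no restriction | Tabulated if reported |
| Who is observed | All subjects, to end of treatment | Only those with an abnormal End of Treatment ACTH test | No end date, so both periods are pooled |

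Follow-up of known events (section 8) explains part of the Day 43/57 collection, since every attendee already has a related suppression event. The serious-event period also covers the first retest: 15 + 30 = Day 45 is after Day 43, and 29 + 30 = Day 59 is after Day 57. It would not cover a second retest 28 days later (15 + 56 = Day 71; 29 + 56 = Day 85). Neither provision says what to do with a new non-serious event.

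**What can change in the tables**

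Each attendee already counts as a subject with an event and with a related event, through the suppression record. The change in those two counts is therefore 0. Rows by system organ class, preferred term, severity and relationship category can change. Relationship rows are included because 8.3.2 has three related categories and 11.5.5 takes the greatest within each classification.

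**Size**

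There is no protocol figure to reproduce. Section 11.1 gives 25 per arm without statistical justification, and section 11 plans no inferential testing.

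Inputs:
- n = 25 per arm (11.1).
- Adult suppression rates p (section 1): 5/24 at 15 days and 0/24 at 29 days. That they carry over to adolescents is an assumption.
- r = proportion of attendees with a new non-serious event over the 28 days. The documents give no figure; 5%, 10% and 20% are assumed.

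Exact (Clopper-Pearson) 95% limits: 5/24 = 20.83% (7.13% to 42.15%); 0/24 = 0% (0% to 14.25%).

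Expected attendees = 25 × p:
- 15-day arm: 25 × 0.2083 = 5.21 (1.78 to 10.54)
- 29-day arm: 0 (0 to 3.56)

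Subjects added to the detailed rows = 25 × p × r, and the same divided by 25 as percentage points:

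| r (assumed) | 15-day arm: subjects (limits) | 15-day arm: points | 29-day arm: subjects (upper limit) |
|---|---|---|---|
| 5% | 0.26 (0.09 to 0.53) | 1.0 | 0 (0.18) |
| 10% | 0.52 (0.18 to 1.05) | 2.1 | 0 (0.36) |
| 20% | 1.04 (0.36 to 2.11) | 4.2 | 0 (0.71) |

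**Equal-rates case**

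If both arms had the same p and the same r, each would gain the same 25 × p × r subjects. For example, p = 20% and r = 10% give 25 × 0.20 × 0.10 = 0.5 in each arm, and no arm difference. An arm difference needs suppression or event rates that differ by arm.

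**The case against.** The strongest reply is that step 4 of 7.9.6 has a purpose consistent with 8.1. It lets sites follow the suppression event and other related events to outcome, and pick up serious events within 30 days. That is a fair account of why the step exists, and it narrows the conflict to new non-serious events. It does not remove it, because neither the step nor the schedule cell is confined to known or serious events, although the same row is restricted where a restriction was meant.

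A second reply is that late events reach the tables only if sites follow 7.9.6 and if the separate SAP promised in section 11 sets no cut-off. This stands, and the table consequence is conditional on both.

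A third is that observation is already unequal by design: 25 × 15 = 375 against 25 × 29 = 725 treatment subject-days, a gap of 350. The conditional visits would add about 5.21 × 28 = 146 subject-days on adult rates. This also stands; closing the window at End of Treatment leaves that larger gap in place. The difference is that treatment length is assigned by randomization, whereas the extra follow-up is triggered by the primary outcome.

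Mitigations in the text also count. Symptoms of suppression would normally be recorded under that diagnosis, and the listings show onset day, so a reader could identify late events.

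A reader might infer more: that the overall adverse event incidence of one arm would be inflated, that the arms would necessarily be unbalanced, or that the primary result is compromised. The documents do not support this. Attendees are already counted as having an event, the imbalance rests on carrying over adult rates, and the primary proportion is fixed at the End of Treatment test.

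**Conclusion.** The inconsistency between 8.1 on one side and 7.9.6 with both schedules on the other is real, and following known events to outcome does not settle it. Because 11.5.5 has no end date, following 7.9.6 would put events from suppressed subjects only into the by-arm rows, unless the unseen SAP prevents it. Following 8.1 would lose those events.

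The consequence is small and descriptive: about 0.26 to 1.04 subjects (1.0 to 4.2 percentage points) in the 15-day arm's detailed rows and 0 in the 29-day arm. This assumes that adult suppression rates carry over and that 5% to 20% of attendees have a new event. Allowing for the exact limits on the adult rates, the range is 0.09 to 2.11 subjects in the 15-day arm and at most 0.71 in the 29-day arm. The point is worth correcting because it is cheap and because ascertainment of events should not depend on the primary outcome.

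**What to change.** 1. Reconcile 8.1 with 7.9.6 and the two schedules under one stated rule for adverse events first found at the conditional visits, so that every site records the same thing.
2. In 11.5.5, limit the by-arm treatment-emergent table to first dose through the End of Treatment evaluation, or the early-withdrawal evaluation under 7.6. Include HPA axis suppression found at that visit. The early-withdrawal evaluation is done only where possible, so observation to that point will not be perfectly complete.
3. Show events first found at the conditional follow-up visits in a separate listing or table, labelled as coming only from subjects with an abnormal End of Treatment test.
4. Keep serious event reporting as in 8.1. State in the report that post-treatment serious events rest on spontaneous reports, with an extra questioned visit only in suppressed subjects, so they are not equally ascertained.

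If the separate SAP already sets a cut-off for the by-arm table, reconciling 8.1 with 7.9.6 and the schedules remains, together with the separate labelling of later events if the SAP does not provide it.

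Cost: wording in 8.1, 7.9.6, the schedules and 11.5.5, plus one labelled output. No new visit, assessment or subject is needed. The downside is that late events, including any product-related ones, leave the main by-arm table, though they remain reported separately. The unequal 15- and 29-day treatment periods remain by design.
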